#### 2.3.3. Definitions and Terminology

#### Study Drug

The term study drug refers to either voxelotor or placebo.

#### Baseline Value

Baseline for all assessments other than laboratory or vital sign parameters, will be defined as the last available pre-treatment value taken on or before the day of randomization and will be used for summary of baseline characteristics and change from baseline analyses, as appropriate.

Baseline for a given laboratory parameter will be defined as the average of all non-missing laboratory values on or prior to the randomization Date.

Baseline for a given vital sign parameter will be defined as the average of all non-missing vital sign value on or prior to randomization Date.

#### Study Day

Study Day is defined relative to the date of randomization.

For study assessments or events that occur on or after the date of randomization, study day is calculated as:

Study 
$$Day = Event Date - Day 1 date + 1$$
.

For study assessments or events that occur before the date of randomization, study day is calculated as:

Study Day = Event Date 
$$-$$
 Day 1 date.

#### Study Visit

Study Visit is the nominal visit as recorded on the CRF.

#### Change from Baseline

Change from baseline for a given endpoint is defined as the Study Day value minus the Baseline value.

#### On-treatment period:

On-treatment period is defined as the time from the first dose of study drug through minimum of 28 days + last dose of study drug and the date of study completion/discontinuation.

#### Extent of exposure to study drug

Extent of exposure to study drug is defined as the number of weeks from initiation of study drug to the end of study drug treatment. Extent of exposure is calculated as follows:

## Actual exposure to study drug

Actual exposure to study drug is defined as the number of weeks from initiation of study drug to the last date of dosing of study drug which excludes days where treatment was

entirely missed or intermittently stopped as recorded in the CRF. Duration of study drug exposure is calculated as follows:

$$\frac{\sum_{i=1}^{n} (End \ Date \ of \ Dose_{i} - Start \ Date \ of \ Dose_{i} + 1) \times I_{Dose_{i}}}{7}$$

where n is the number of dose modifications during the study and

$$I_{Dose_i} = \begin{cases} 0 \text{, if treatment dose } i = 0 \text{ mg} \\ 1 \text{, if treatment dose } i \neq 0 \text{ mg'} \end{cases} i = 1, 2, ..., n.$$

# 3. ENDPOINTS AND BASELINE VARIABLES: DEFINITIONS AND CONVENTIONS

## 3.1. Primary Endpoint(s)

The proportion of participants achieving resolution of the target ulcer(s), during the 12-week Randomized Treatment Period.

For participants with more than one target ulcer, all target ulcers must be confirmed resolved in order for the participant to be considered a responder.

A target ulcer can be defined as following criteria:

CCI

 Size: > 2 cm^2 at any visit, prior to randomization (Visits 1, 2, and 3, using central reader measurement)

If the ulcer does not meet the criteria above, it will not be used as the target ulcer for the efficacy analysis.

## 3.2. Secondary Endpoint(s)

Time (in days) to resolution of target ulcer(s) up to Week 12

Time to resolution of target ulcer(s) is defined as

Date of resolution – Date of randomization +1,

where the date of resolution is defined as the first time of the observed ulcer was resolved. For participants with more than one target ulcer, time to resolution of target

> PFIZER CONFIDENTIAL TMF Doc ID: 98.03 Page 16 of 43

[figure not shown]
ulcer(s) is defined as time to the last target ulcer confirmed resolved. For participants who do not have the last target ulcer confirmed resolved by Week 12 or who are discontinued from study, the time to resolution will be censored.

- Change from baseline in total surface area of target ulcer(s) at Week 12
- Incidence of new ulcers by Week 12

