## 8.4.2. Secondary Endpoints

Time to resolution of target ulcer(s) up to Week 12: a stratified log-rank test will be used to compare the treatment groups. A Cox regression model will be used to estimate the hazard ratio between voxelotor +SOC and placebo + SOC groups, as appropriate. Time to resolution will be measured (in days) from Day 1 to date of initial closure of the target ulcer. For participants with more than one target ulcer, time to resolution will be based on the time to closure of all target ulcers (ie, initial closure of the last target ulcer to resolve).

Change from baseline in sum of surface area of target ulcer(s) at Week 12: a mixed-effect model for repeated measures will be used to estimate and compare change from baseline in sum of target ulcer(s) surface area between voxelotor + SOC and placebo + SOC groups. The model will include terms for treatment group, study visit, treatment-by-study visit interaction, as well as the stratification factors. Within-participant variability will be modeled using an unstructured covariance matrix.

Incidence of new ulcers by Week 12: the proportion of participants with new ulcer occurrence within 12 weeks of treatment will be compared between treatment groups using a CMH test, stratified by target ulcer size, and target ulcer duration, as appropriate.

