Visit Number (Week)	Visit 1 (Week -6 to - 2)	Visit 2 (Week -2)	Visit 3 (Week 0)	Visits 4-8 b (Week 2-10)	Visit 9 (Week 12)	Visit 10-14° (Week 14- 22)	Visit 15 (Week 24)	Visit 16-A & onward d (Week 28)	Visit 16-B (Week 28)	
Visit Day	-42 to -14	-14	Day 1	Day 14-70	Day 84	Day 96-154	Day 168	Day 196 & onward	Day 196	
Visit Window	_	+3 days	+1 day	±3 days	±3 days	±3 days	±3 days	±5 days	±7 days	_

- t. Study drug will be dispensed at the Day 1, Week 6, Week 12, and Week 18 visits. For participants who continue to receive voxelotor beyond 12 weeks in the Open-label Treatment Period (See Section 5.1), study drug will be dispensed every 12 weeks.
- Participants demonstrating initial ulcer-re-epithelization at Week 12 will continue treatment in their assigned treatment group for an additional 2 weeks to confirm ulcer resolution.
- v. Participants transitioning to a program providing voxelotor through an alternative source will complete assessments on the day they transition to that program. Study drug for this study should not be taken on the day of that visit (dose will be taken on that day as part of the alternative source program).
- w. Only required for participants transitioning to a program providing voxelotor through an alternative source

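### SAP 3.2 can be read as dating resolution at confirmation for participants with several target ulcers, against the protocol's initial closure, and its censoring clause is too wide; the effect on this secondary endpoint is small

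*SAP*

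**What the plan says.** **Protocol 8.4.2** has one rule. "Time to resolution will be measured (in days) from Day 1 to date of initial closure of the target ulcer"; for several target ulcers the event is the "initial closure of the last target ulcer to resolve".

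**SAP 3.2** gives a general formula, date of resolution minus date of randomization plus 1, "where the date of resolution is defined as the first time of the observed ulcer was resolved". It then adds a sentence for participants with more than one target ulcer, for whom time to resolution of target "ulcer(s) is defined as time to the last target ulcer confirmed resolved". Censoring applies to participants who "do not have the last target ulcer confirmed resolved by Week 12 or who are discontinued from study". SAP Appendix 1 repeats the censoring rule.

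**SAP 2.1** lists no modification of the protocol's analysis.

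**Confirmation timing.** Under Protocol Appendix 1, participants whose ulcer first re-epithelializes at Week 12 stay on assigned treatment "for an additional 2 weeks to confirm ulcer resolution". SAP 2.3.2 extends their randomized reporting period to Week 14 for this purpose. Ulcer visits are every 2 weeks (Protocol 3.1).

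**Analysis.** All ITT participants enter one stratified log-rank test and one stratified Cox model (SAP 5.2.3 and 6.2). The strata are total ulcer size and longest ulcer duration (SAP 3.4.1); number of ulcers is not among the factors shown.

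**The concern.** Three things in SAP 3.2 do not fit together.

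1. Read word for word, a participant with one ulcer has the event at first closure, and a participant with several has it at the confirmation visit of the last one. One analysis would then hold two kinds of date, against the protocol and without a declared change.
2. The words "or who are discontinued from study, the time to resolution will be censored" carry no condition that the departure comes before resolution. A participant with confirmed closure who later leaves is a responder for the primary endpoint but, read literally, censored here. The primary rule does carry the condition: only dropout without confirmed resolution makes a non-responder (Protocol 8.4.1, SAP 5.3.1). SAP 2 records a dosing pause and study termination, so later departures are plausible. The documents do not say how many confirmed responders were affected.
3. Requiring confirmation by Week 12 censors a closure first seen at Week 12 and confirmed at Week 14, although SAP 2.3.2 extends the period to confirm exactly that closure.

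At stake are the Kaplan-Meier times, the hazard ratio and reproducibility: two programmers could build different datasets from this text.

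**Working it through.** **The plan's own figure.** The documents give no power or event count for time to resolution. The only design figure is about 90% power for a 35-point difference in the primary endpoint at 40 per arm (Protocol 8.6). Pooled normal approximation:

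power = Φ{[Δ − 1.96·√(2p̄(1−p̄)/n)] / √[(p₁q₁+p₂q₂)/n]}

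At 20% vs 55%: (0.35 − 1.96 × 0.1083)/0.1009 = 1.37, so power is 0.914. Over control rates of 20% to 45% it is 0.894 to 0.914, which agrees with the plan. The control rate is not visible, so the rates below are assumptions.

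**Gap between the two dates.** From SAP Appendix 2.1, Week 12 is Day 84 (81 to 87) and Week 14 is Day 98 (95 to 101). Nominal gap: 98 − 84 = 14 days. Range within windows: 95 − 87 = 8 to 101 − 81 = 20 days. This is explicit only for closure first seen at Week 12. For earlier closures 14 days is inferred from the visit spacing, because the full definition of resolution is redacted.

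**Shift in mean time and events lost.** Assumptions: exponential closure with proportion p closed by Day 84, visits at day 14k (k = 1 to 6), share m with several ulcers, the same in all closers. The probability of first closure seen at visit k is f_k = (1−p)^((k−1)/6) − (1−p)^(k/6).

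- Protocol rule: mean = Σ14k·f_k / p.
- Literal SAP rule: multi-ulcer events move to 14(k+1), and those with k = 6 fall at about Day 98 and are censored. Mean = [(1−m)Σ14k·f_k + mΣ_{k≤5}14(k+1)f_k] / [p − m·f₆].
- Share of events lost = m·f₆/p.

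| p | f₆ | mean, protocol | mean, m = 30% | mean, m = 50% | events lost, 30% / 50% |
|---|---|---|---|---|---|
| 20% | 0.0303 | 47.5 | 49.5 (+2.0) | 50.9 (+3.4) | 4.5% / 7.6% |
| 55% | 0.0641 | 43.6 | 46.0 (+2.4) | 47.7 (+4.1) | 3.5% / 5.8% |

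**Log-rank test.** Simulation with the same visit model, 40 per arm, a 35-point difference, unstratified test and 3000 runs per cell:

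| Control rate | First closure for all | 20% multi-ulcer, mixed dates | 40% multi-ulcer, mixed dates |
|---|---|---|---|
| 10% | 0.960 | 0.956 | 0.959 |
| 20% | 0.923 | 0.912 | 0.899 |
| 30% | 0.904 | 0.909 | 0.887 |

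The largest fall is 0.923 − 0.899 = 0.024; the simulation standard error of each entry is about √(0.9 × 0.1/3000) = 0.005. Between 0.6 and 1.8 events per trial become censored, out of about 22 to 38. Under the null (30% in both arms, 40% multi-ulcer) the rejection rate is 0.051, against 0.050 with first closure for all.

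**If the Week 12 clause also reaches single-ulcer participants.** Every closure first seen at Week 12 is then lost: f₆/p = 0.0641/0.55 = 11.7%, or 0.0303/0.20 = 15.2%. Using confirmation dates for everyone on the 84-day horizon loses the same events and otherwise keeps their order. Its simulated power was 0.929, 0.884 and 0.865, a fall of 3 to 4 points.

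**The case against.** The strongest reply is that SAP 3.2 has one formula for everyone, and its date is the first time the ulcer was seen resolved. The multi-ulcer sentence may only say which ulcer governs. Being confirmed resolved is also how both documents describe a responder's status (Protocol 3.1.3.1 and 8.4.1, SAP 3.1). On that reading SAP and protocol agree, and the empty SAP 2.1 fits. This stands as a possible reading, but the SAP does not state it and the literal wording gives the other.

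A second reply is that ordinary practice never censors a participant after the event. That is fair, and the clause may be loose drafting. It appears twice without the qualifier that the parallel dropout rules carry, so it still needs correcting.

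A reader might infer more than the documents support:

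- **That mixed dates are certain, or that 14 days applies to every multi-ulcer closer.** The text is ambiguous, and the gap is inferred for closures before Week 12.
- **That mean time rises by 4 to 7 days.** That is 0.3 × 14 = 4.2 to 0.5 × 14 = 7.0. It ignores that, under the same literal reading, Week 12 multi-ulcer closers are censored and leave the mean.
- **That the Kaplan-Meier median moves from Day 56 to Day 70.** This happens at 65% healing only because cumulative closure at Day 56 is then 50.3%, so almost any delay moves it one visit. At 55% it does not move.
- **That the hazard ratio shifts materially.** With an assumed 50% vs 30% imbalance in multi-ulcer share, two simulations gave 3.4 to 3.2 and 3.64 to 3.53. With 8 and 22 events, the standard error of log HR is √(1/8 + 1/22) = 0.41, so a 95% interval around 3.4 runs from about 1.5 to 7.6. The shift is negligible beside that.

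**Conclusion.** The point holds as a definition to reconcile. Read literally, SAP 3.2 departs from Protocol 8.4.2 for participants with several target ulcers, and its censoring clause is wider than the primary rule and at odds with SAP 2.3.2. The primary endpoint and the sample size are untouched.

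With multi-ulcer shares of 30% to 50% and exponential closure, the mixed dates add about 2 to 4 days to mean time among events and turn roughly 3% to 8% of events into censored times. The simulations, run at shares of 20% and 40%, show no type I inflation and at most about 2 points of power lost. If the Week 12 clause were also applied literally to single-ulcer participants, the loss would be 3 to 4 points. The multi-ulcer share, the healing rates and the healing curve are assumptions, since the documents give none of them. Censoring of confirmed responders who later leave is not in these figures, because their number is not stated.

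**What to change.** - **SAP 3.2, event date.** For one or several target ulcers, define it as the date of initial closure of the last target ulcer to close, given that closure is later confirmed. Say that this includes a Week 12 closure confirmed at Week 14.
- **SAP 3.2 and Appendix 1, censoring.** Censor only participants without an initial closure by Week 12 that is later confirmed, or who discontinue from the study before confirmed resolution.
- **If the confirmation date is intended,** apply it to all participants, state how a Week 12 closure is counted, and declare the change in SAP 2.1.

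The cost is two sentences, one of them repeated in Appendix 1, and no new data. If the derivation is already programmed, the study report should state which date was used.

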## Open-label Treatment Period (minimum 12 weeks $[\pm 3$ -day window for each visit])

At the end of the 12-week Randomized Treatment Period, all participants (with the exception of those demonstrating initial ulcer re-epithelialization at Week 12) will receive open-label voxelotor 1500 mg per day and SOC for a minimum of 12 weeks and target ulcers that failed to heal during the initial 12 weeks will be followed for delayed healing. Assessments will continue to be performed per the SOA (Appendix 1).

Note: Participants who have completed 12 weeks in the Open-label Treatment Period may continue to receive voxelotor as long as they continue to receive clinical benefit that outweighs risk as determined by the Investigator or until the participant has access to voxelotor from an alternative source (eg, through a clinical OLE study sponsored by Pfizer, commercialization of the product, or a managed access program). Participants who do not plan to continue to receive voxelotor from an alternative source should continue to the follow-up period after completing 12 weeks in the Open-label Treatment Period.

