## 2.3.2. Treatment Group and Reporting Period for Analysis

In the study schematic in Figure 1. Study Schema, the study period and treatment groups to be included in the primary and open-label analysis.

Efficacy and Safety: Primary analysis (Randomized Treatment Period):

- Treatment groups:
  - Voxelotor: participants randomized to voxelotor.
  - Placebo: participants randomized to placebo.
- Reporting Period:
  - From Day 1 through Week 12 for subjects who either do not achieve confirmed reepithelialization or achieve it before or at Week 12 visit.
  - From Day 1 through Week 14 for subjects who have the initial skin reepithelialization confirmed at Week 12 and then the 14-week visit will be used to confirm resolution.

Day 1 is defined as the date of randomization. The last day (i.e. Week 12 visit or Week 14) of randomized treatment period is defined as the last day entered on the disposition page for end of randomized treatment period.

Efficacy: Open-label analysis (Open-Label Treatment Period):

- Treatment groups:
  - Voxelotor: participants randomized to voxelotor who received at least one dose of voxelotor.

- Delayed voxelotor: participants randomized to placebo during Randomized Treatment Period (through Week 12) and who received at least one dose of voxelotor on or after the Week 12 visit.
- Total: participants who received at least one dose of voxelotor.

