## Reporting Period:

- After Week 12 (one day after Week 12 visit) through Week 24 for subjects who either
  do not achieve confirmed re-epithelialization or achieved it before or at Week 12
  visit.
- After Week 14 (one day after Week 14 visit) through Week 24 for subjects who have the initial skin re-epithelialization confirmed at Week 12 and then the 14-week visit will be used to confirm resolution.

Safety: Open-label analysis (Open-Label Treatment Extension Period which is combining the entire Open-Label Treatment Period and the Follow-up Period):

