# APPENDICES

# Appendix 1. Summary of Efficacy Analyses

Endpoint	Analysis Type	Population	Data Inclusion and Rules for Handling Intercurrent Events and Missing Data	Main Analysis Model
Primary				
The status of participants achieving resolution of the target ulcer(s) by Week 12	Exact CMH test Descriptive summary statistics Subgroup analysis	ITT	Participants who are lost to follow-up or otherwise drop out of the study without confirmation of resolution of all target study ulcer(s) prior to Week 12, will be classified as non- responder.	Exact CMH test with stratification factors of target ulcer size and duration
Secondary				
Time (in days) to resolution of target ulcer(s) up to Week 12	Log-rank and Cox regression model  Descriptive summary statistics  Subgroup analysis	ITT	For participants who do not have the last target ulcer confirmed resolved by Week 12 or who are discontinued from study, the time to resolution will be censored	Kaplan-Meier method (product-limit estimates) and estimated survival curves will be displayed graphically when appropriate. Graphs will describe the number of participants at risk over time. A stratified log-rank test with stratification factors will be performed to test for differences between the voxelotor and placebo treatment groups
Change from baseline in total surface area of target ulcer(s) at Week 12	LS means (95%CI) LS means difference Descriptive summary statistics Subgroup analysis	ITT	NA	MMRM analysis will be used as described in Section 5.2.2.1 with the stratification factors including target ulcer size (categorical) and target ulcer duration (categorical) as covariates and. The p-value for LS means difference (voxelotor vs. placebo) at Week 12 will be provided.

Endpoint	Analysis Type	Population	Data Inclusion and Rules for Handling Intercurrent Events and Missing Data	Main Analysis Model
Incidence of new ulcers by Week 12	Exact CMH test Descriptive summary statistics Subgroup analysis (age group and country)	ITT	NA	Exact CMH test with stratification factors of target ulcer size and duration
Exploratory				
The proportion of participants achieving resolution of the target ulcer(s) by Week 24	Descriptive summary statistics	ITT	NA	Descriptive statistics
Time (in days) to resolution of target ulcer(s) up to Week 24	Descriptive summary statistics	ITT	NA	Descriptive statistics

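### Time to resolution: as written, the SAP censors a closure first seen at Week 12 and confirmed at Week 14, although the plan keeps Week 14 in the randomized period to confirm such closures

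*SAP*

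**What the plan says.** **The censoring rule.** SAP 3.2 censors time to resolution for participants who "do not have the last target ulcer confirmed resolved by Week 12" and for those who leave the study. SAP Appendix 1 repeats the rule, ending "who are discontinued from study, the time to resolution will be censored". Neither place gives a censoring date.

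**The event date.** Protocol 8.4.2 measures time "from Day 1 to date of initial closure of the target ulcer"; with several target ulcers, it uses the initial closure of the last one. SAP 3.2 also dates resolution at the first time the ulcer was observed resolved.

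**What happens to a closure first seen at Week 12.**
- Protocol 3.1 sends all participants to open-label treatment at Week 12, "with the exception of those demonstrating initial ulcer re-epithelialization at Week 12".
- A Week 12 footnote to the Protocol Appendix 1 schedule says that these participants "will continue treatment in their assigned treatment group for an additional 2 weeks to confirm ulcer resolution".
- SAP 2.3.2, under the heading that begins "Efficacy and Safety: Primary analysis (Randomized Treatment Period", ends the reporting period at Week 12 for those never confirmed and for those confirmed before or at Week 12. It runs the period to Week 14 for those whose initial re-epithelialization is "confirmed at Week 12 and then the 14-week visit will be used to confirm resolution".
- Their open-label reporting period is "After Week 14 (one day after Week 14 visit) through Week 24 for subjects who have the initial skin re-epithelialization confirmed at Week 12".

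**The concern.** The plan sets up a Week 14 confirmation for closures first seen at Week 12, on assigned treatment and inside the randomized reporting period. The censoring sentence, followed as written, then discards those closures for the first-listed secondary endpoint, which has a stratified log-rank p-value and a Cox hazard ratio.

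Two competent programmers could build different event sets from the same text. If the literal rule is programmed, and the primary analysis counts Week 14 confirmations as SAP 2.3.2 indicates, some primary responders appear as censored in the time-to-resolution analysis. The two results would then disagree on who healed.

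**Working it through.** **Step 1: can a closure first seen at Week 12 be confirmed by Week 12?** SAP Appendix 2.1 gives analysis windows of Days 78 to 91 for Week 12 and Days 92 to 105 for Week 14. They do not overlap. The protocol footnote puts confirmation 2 weeks after Week 12, so it falls in the Week 14 window. Under the literal rule the participant is censored, although Protocol 8.4.2 would date the event at Week 12.

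**Step 2: is the literal reading natural?** SAP 2.3.2 itself treats confirmation before or at Week 12 as one group and initial closure at Week 12 with Week 14 confirmation as another. Carried into SAP 3.2, that usage censors the second group.

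**Step 3: the plan's own figure.** No power is stated for time to resolution. The only design figure is about 90% power for the primary endpoint (40 per arm, 35-point difference, two-sided 5%). The control rate is not visible. At an assumed 25% vs 60%, with the pooled normal approximation:
- null SE = √(2 × 0.425 × 0.575 / 40) = 0.1105
- alternative SE = √((0.25 × 0.75 + 0.60 × 0.40) / 40) = 0.1034
- z = (0.35 − 1.96 × 0.1105) / 0.1034 = 1.29, so power = 0.901

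Control rates of 20 to 40% give 0.895 to 0.914. The stated figure therefore fits many control rates, and the point does not depend on which one was used.

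**Step 4: how many closures are affected (illustration).** Assume a constant healing hazard, 40 per arm, visits every 2 weeks (six to Week 12), no dropout, and confirmation one visit after closure throughout. With healing rate p by Week 12, the proportion first seen closed by Week 10 is 1 − (1 − p)^(5/6).
- Control, p = 0.25: 1 − 0.75^(5/6) = 0.213. First seen at Week 12: 0.250 − 0.213 = 0.037, or 1.5 of 40.
- Voxelotor, p = 0.60: 1 − 0.40^(5/6) = 0.534. First seen at Week 12: 0.600 − 0.534 = 0.066, or 2.6 of 40.
- Together: 4.1 of 34 expected healers, about 12%.

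Under the literal rule the Week 12 Kaplan-Meier estimates would read 21.3% and 53.4%, against response rates of 25% and 60%.

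**Step 5: effect on the log-rank test.** Unstratified test, constant hazard, 20,000 simulated trials per row:

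| Assumed healing by Week 12 | Share of healers first seen at Week 12 (control, voxelotor) | Healers censored, both arms | Power: counted → censored |
|---|---|---|---|
| 10% vs 45% | 15.9%, 12.8% | 2.9 | 0.959 → 0.930 |
| 25% vs 60% | 14.7%, 11.0% | 4.1 | 0.905 → 0.863 |
| 40% vs 75% | 13.3%, 8.7% | 4.7 | 0.916 → 0.885 |
| 50% vs 85% | 12.2%, 6.6% | 4.7 | 0.958 → 0.940 |

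The shares are of healers, not of participants. A stratified version (four equal strata, 5% dropout, both assumed in form) loses about 2 to 5 points.

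**Step 6: sensitivity to the time course.** With decelerating healing (Weibull shape 0.5), 1.5 to 2.4 healers are censored and the unstratified loss is about 1 to 2 points. With accelerating healing (shape 2), the figures are 5.6 to 9.4 healers and about 5 to 10 points.

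**The case against.** The strongest reply is that the SAP already handles the case and the sentence is only loosely drafted. The definition of resolution is redacted wherever it would appear, and a Week 14 rule could sit there. SAP 2.3.2 covers efficacy generally, not just the primary endpoint. It also uses the word confirmed for the initial closure at Week 12. SAP 3.3 equates confirmed re-epithelialization by Week 12 with achieving resolution, and SAP 3.2 dates the event at first observation. On this view the phrase means closed by Week 12 and confirmed later, and the mismatch with the primary analysis arises only if 2.3.2 is ignored for one endpoint.

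Much of this stands. The softer reading is coherent, and because of the redaction one can say only that no visible text applies it to this endpoint. The reply does not remove the problem: the censoring sentence is visible, appears twice, and points the other way, and 2.3.2 also separates the two groups in a manner that supports the literal reading.

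It is also fair that the power figures rest on assumptions. With the last visit already past, they describe the size of the ambiguity and are not design quantities.

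A reader might infer a second error: that with several ulcers SAP 3.2 dates healing at confirmation, against Protocol 8.4.2. The documents do not support treating it as one. The preceding SAP sentence dates resolution at first observation, and Protocol 3.1.3.1 uses the confirmed wording for responder status.

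**Conclusion.** Wrong as written; minor to moderate. Followed literally, the rule in SAP 3.2 and Appendix 1 censors closures that SAP 2.3.2, Protocol 3.1 and the Protocol Appendix 1 footnote keep in the randomized period for confirmation, and that Protocol 8.4.2 would count from initial closure.

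Under the assumed rates and a constant hazard, about 3 to 5 healers are censored and about 2 to 4 points of log-rank power are lost. Without dropout, the Week 12 Kaplan-Meier estimate then falls below the primary response rate, provided the primary analysis counts Week 14 confirmations. Dropout muddies that comparison, because the primary analysis counts dropouts as non-responders while Kaplan-Meier censors them.

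Three stronger readings are not supported:
- That these closures will certainly be lost. A coherent alternative reading exists, and part of the definition is redacted.
- That the primary result is at risk. This rule does not enter the primary test.
- That the loss is 5 to 10 points. That needs accelerating healing, for which the documents give no evidence.

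**What to change.** In SAP 3.2 and Appendix 1, define the event as initial closure of the last target ulcer on or before the Week 12 visit that is later confirmed (at Week 14 when first seen at Week 12), dated at initial closure. Censor all others at their last ulcer assessment up to Week 12. The same sentence settles the dating for several ulcers and supplies the missing censoring date. If the literal rule is what the sponsor intends, declare it in SAP 2.1, which now reports no modifications to the protocol's analysis plan.

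The cost is one sentence in two places and a check of the event rule in programming; no new data are needed. This SAP version is dated 16-Dec-2024 and last subject last visit was 22 October 2024. The clarification should therefore be dated and recorded as made after last visit, with a statement of whether treatment assignments were known at the time, which the documents do not say.
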